9.5. Physical Examination

Physical examinations will be performed at each visit. The body systems will be examined, and the findings will be classified as “Normal”, “Abnormal, Not Clinically Significant” and “Abnormal, Clinically Significant”. A shift table comparing the categorical results at each scheduled post-baseline visit with those at baseline will be summarized overall and by body system. All physical examination data will be listed by visit [Screening, Day 1 (Week 0), Day 15 (Week 0), Week 4, Week 8 Week 12 (EOS/EOT) and Week 26] and body system for safety population.

9.6. Electrocardiogram

12-lead ECGs will be performed at screening, Week 12 (EOS/ET) and Week 26 visits and interpreted as “Normal”, “Abnormal, Not Clinically Significant” and “Abnormal, Clinically Significant”. A shift table comparing the interpretation at scheduled post-baseline visit with those at baseline will be presented by visit for the safety population.

A summary table with actual values and change from baseline will be presented for ECG parameters (ventricular rate, P-R interval, QRS duration, Q-T interval, QTcF) by scheduled visit.

The reference ranges for Ventricular rate: 60 - 100 beats/min; P-R interval: 120 – 200 msec; QRS duration: 80 – 120 msec; QTcF: \leq 450 msec. Based on the ranges the parameters will be interpreted as below.

- Abnormal Low
- Normal
- Abnormal High

All ECG data will be listed by visit for safety population.

9.7. Pregnancy Test

For subjects of childbearing potential, serum pregnancy test will be performed at screening, Week 12 EOS/ET and week 26 visit. A urine pregnancy test will be performed to confirm subjects are not pregnant on Day 1 prior to randomization and Day 15 before dosing and at week 2, week 4 and week 8 visits. The results will be classified as “Positive” or “Negative”. Serum pregnancy test results will be listed for safety population.

10. Changes in the Planned Analysis

12.1. Schedule of Study Procedures

Study Period	Screening Visit Days -14 to 0	Treatment Visit		Follow-Up Visits		EOS/ET ^a Visit	Additional Follow-up Visit ^m
Study Week		0 (Day 1)	2 (Day 15)	4	8	12	26
Visit Window		+1 day	+1 day	±7 days			
Informed consent ^b	X	-	-	-	-	-	-
Inclusion/exclusion criteria ^c	X	X ^k	-	-	-	-	-
Medical and surgical history	X	-	-	-	-	-	-
Prior and ongoing medication	X	-	-	-	-	-	-
Demographics	X	-	-	-	-	-	-
TB screening (if required) ^d	X	-	-	-	-	-	-
Viral disease screening ^e	X	-	-	-	-	-	-
Physical examination ^f	X	X	X	X	X	X	X
Vital signs measurements ^g	X	X	X	X	X	X	X
12-lead ECG	X	-	-	-	-	X	X
Pregnancy test ^h	X	X	X	X	X	X	X
Clinical laboratory assessments ⁱ	X	X ^l	X	X	X	X	X
Randomization	-	X	-	-	-	-	-
Study treatment administration	-	X	X	-	-	-	-
Adverse events	X	X	X	X	X	X	X

Study Period	Screening Visit Days -14 to 0	Treatment Visit		Follow-Up Visits		EOS/ET ^a Visit	Additional Follow-up Visit ^m
Study Week		0 (Day 1)	2 (Day 15)	4	8	12	26
Visit Window		+1 day	+1 day	±7 days			
Immunogenicity ^j	-	X	X	X	X	X	-
Blood sample for estimation of rituximab concentration	-	X	X	X	X	X	-
Concomitant medications	-	X	X	X	X	X	X

Abbreviations: ADA, anti-drug antibody; ECG, electrocardiogram; EOS, end of study; ET, early termination; EU-rituximab, European Union approved rituximab (MabThera); HBcAb, hepatitis B core antibody; HBsAg, hepatitis B surface antigen; HCV, hepatitis C virus; HIV, human immunodeficiency virus; IgG, immunoglobulin G; IgM, immunoglobulin M; NAb, neutralizing antibody; TB, tuberculosis; US-rituximab, United States-licensed rituximab (Rituxan).

Note: For assessments related to COVID-19, see [Section 3.2](#) of the protocol.

- ^a All subjects completing the study at Week 12 or those discontinuing the study at any time will attend an EOS/ET visit. The allowable window for the EOS/ET visit is ± 7 days.
- ^b Informed consent must be obtained prior to undergoing any protocol-specific procedure.
- ^c All eligibility criteria must be met before a subject is randomized to study treatment. Subjects must have received at least 1 full course comprising two 1000 mg infusion of either US-rituximab at least 16 weeks or EU-rituximab at least 24 weeks prior but not more than 15 months prior to the day of randomization visit.
- ^d Tuberculosis testing is to be done only if it is required by local regulations or practice.
- ^e The following tests are to be conducted by each site's local laboratory: HBsAg, HBcAb, HCV, HIV, serum IgG and IgM.
Note: For HBcAb, site is requested to perform HBcAb IgG and HBcAb IgM. If any of these 2 results is positive, then the subject will be considered as screen failure.
- ^f Complete physical examination will be performed at all visits. Height will be recorded at screening only.
- ^g Body temperature (oral), blood pressure, heart rate, and respiration rate will be recorded at each visit. Vital signs will be monitored every 30 minutes (± 5 minutes) during the course of the treatment administration or more frequently as necessary.
- ^h Subjects who are WOCBP will have a serum pregnancy test at the screening visit, Week 12 (EOS/ET), and Week 26 (additional follow-up) and a urine pregnancy test on Day 1 prior to randomization and Day 15 (before dosing), Week 4, and Week 8 visits. All tests will be performed by the local laboratory according to local practice.
- ⁱ Clinical laboratory assessments (hematology/biochemistry/urinalysis) will be performed by the local laboratory. See [Section 6.3.4](#) for the list of tests.
- ^j Plasma samples for detection of ADA will be collected before the administration of study treatment on Day 1 and Day 15 (preferably within 30 minutes prior to infusion). Additional samples for detection of ADA will be collected at Weeks 4, 8, and 12 (EOS/ET). Samples that are confirmed positive for ADA will be further tested for titer and NAb. Details are provided in [Section 6.2](#).
- ^k Viral disease screening (HBsAg, HBcAb, HCV, and HIV), serum IgG and IgM, and TB screening will not be repeated on Day 1 of the study.
- ^l Clinical laboratory assessments scheduled on Day 1 can be performed 1 day prior to dosing.
- ^m Additional follow-up visit will be conducted at Week 26 to evaluate safety and to perform a serum pregnancy test in WOCBP.

12.2. Tables and Listings

Tables:

Table No.	Table Title	Analysis Population
14.1.1.1	Summary of Screen Failures	All Subjects
14.1.1.2	Summary of Analysis Sets and Reason for Exclusion	All Randomized Subjects
14.1.1.3	Subject Disposition	All Randomized Subjects
14.1.1.4	Study Deviations	Safety Population
14.1.1.5	COVID-19 or Related Events Study Deviations	Safety Population
14.1.1.6	Missed Visit or Assessment Due to COVID-19 or Related Events	Safety Population
14.1.2.1	Demographics Baseline Characteristics	Safety Population
14.1.3.1	Baseline Disease Characteristics	Safety Population
14.1.4.1	Summary of Viral Serology	Safety Population
14.1.5.1	Summary of Medical and Surgical History	Safety Population
14.1.5.2	Summary of Rheumatic Disease History	Safety Population
14.1.6.1	Summary of Prior Medications	Safety Population
14.1.6.2	Summary of Concomitant Medications	Safety Population
14.1.6.3	Summary of Rescue Medications/Re-dosing Medications	Safety Population
14.1.7.1	Summary of Study Drug Administration	Safety Population
14.2.2.1	Summary of ADA and NaB by Visit and Overall	Immunogenicity Population
14.2.2.1A	Estimand 1: Summary of ADA and NaB by Visit and Overall	Immunogenicity Population
14.2.2.2	Summary of ADA titer by Visit	Immunogenicity Population
14.2.2.2A	Estimand 1: Summary of ADA titer by Visit	Immunogenicity Population
14.2.2.3	Shift from Baseline ADA Positive by Visit ADA Positive at Baseline	Immunogenicity Populations

14.2.2.3A	Estimand 1: Shift from Baseline ADA Positive by Visit ADA Positive at Baseline	Immunogenicity Populations
14.2.2.4	Summary of Time Matched Rituximab Concentration by Visit	TMRC Population
14.3.1.1	Overall Summary of Adverse Events	Safety Population
14.3.1.2.1	Treatment Emergent Adverse Events by System Organ Class and Preferred Term	Safety Population
14.3.1.2.2	Study Drug-Related Treatment Emergent Adverse Events by System Organ Class and Preferred Term	Safety Population
14.3.1.2.3	Treatment Emergent Adverse Events by System Organ Class, Preferred Term and CTCAE Severity	Safety Population
14.3.1.2.4	Serious Treatment-Emergent Adverse Events by System Organ Class and Preferred Term	Safety Population
14.3.1.2.5	Study Drug-Related Serious Treatment-Emergent Adverse Events by System Organ Class and Preferred Term	Safety Population
14.3.1.2.6	Treatment Emergent Adverse Events Leading to Treatment Discontinuation by System Organ Class and Preferred Term	Safety Population
14.3.1.2.7.1	Treatment Emergent Adverse Events classified as Hypersensitivity Reactions by System Organ Class, Preferred Term and Relationship	Safety Population
14.3.1.2.7.2	Treatment Emergent Adverse Events classified as Hypersensitivity Reactions by System Organ Class, Preferred Term and CTCAE Severity	Safety Population
14.3.1.2.7.3	Serious Treatment Emergent Adverse Events classified as Hypersensitivity Reactions by System Organ Class, Preferred Term and Relationship	Safety Population
14.3.1.2.7.4	Serious Treatment Emergent Adverse Events classified as Hypersensitivity Reactions by System Organ Class, Preferred Term and CTCAE Severity	Safety Population
14.3.1.2.8.1	Treatment Emergent Adverse Events classified as Infusion Related Reactions (IRR) by System Organ Class, Preferred Term and Relationship	Safety Population

14.3.1.2.8.2	Treatment Emergent Adverse Events classified as Infusion Related Reactions (IRR) by System Organ Class, Preferred Term and CTCAE Severity	Safety Population
14.3.1.2.8.3	Serious Treatment Emergent Adverse Events classified as Infusion Related Reactions (IRR) by System Organ Class, Preferred Term and Relationship	Safety Population
14.3.1.2.8.4	Serious Treatment Emergent Adverse Events classified as Infusion Related Reactions (IRR) by System Organ Class, Preferred Term and CTCAE Severity	Safety Population
14.3.1.2.9.1	Treatment Emergent Adverse Events classified as Anaphylactic Reactions by System Organ Class, Preferred Term and Relationship	Safety Population
14.3.1.2.9.2	Treatment Emergent Adverse Events classified as Anaphylactic Reactions by System Organ Class, Preferred Term and CTCAE Severity	Safety Population
14.3.1.2.9.3	Serious Treatment Emergent Adverse Events classified as Anaphylactic Reactions by System Organ Class, Preferred Term and Relationship	Safety Population
14.3.1.2.9.4	Serious Treatment Emergent Adverse Events classified as Anaphylactic Reactions by System Organ Class, Preferred Term and CTCAE Severity	Safety Population
14.3.1.2.9.5	Treatment Emergent Adverse Events classified as Anaphylactic Reactions by Sampson's Anaphylaxis Criteria	Safety Population
14.3.1.2.10.1	Study Drug-Related Events of Special Interest (EOSI) by System Organ Class, Preferred Term and CTCAE Severity	Safety Population
14.3.1.2.10.2	Study Drug-Related Serious Events of Special Interest (EOSI) by System Organ Class, Preferred Term and CTCAE Severity	Safety Population
14.3.1.2.11	Treatment Emergent Adverse Events for Rescue Medication by System Organ Class and Preferred Term	Safety Population
14.3.4.1.1	Actual Value and Change from Baseline in Hematology	Safety Population
14.3.4.1.2	Actual Value and Change from Baseline in Chemistry	Safety Population
14.3.4.1.3	Actual Value and Change from Baseline in Urinalysis	Safety Population
14.3.4.1.4	Summary of Neutropenia	Safety Population

14.3.4.2.1.1	Shift from Baseline in Hematology	Safety Population
14.3.4.2.1.2	Hematology Shift Table Based on CTCAE Grade by Parameter	Safety Population
14.3.4.2.2.1	Shift from Baseline in Biochemistry	Safety Population
14.3.4.2.2.2	Biochemistry Shift Table Based on CTCAE Grade by Parameter	Safety Population
14.3.4.2.3	Shift from Baseline in Urinalysis	Safety Population
14.3.4.3.1	Actual Value and Change from Baseline in Vital Signs	Safety Population
14.3.4.3.2	Shift from Baseline in Vital Signs	Safety Population
14.3.4.4	Shift from Baseline in Physical Examination	Safety Population
14.3.4.5.1	Actual Value and Change from Baseline in 12-Lead Electrocardiogram	Safety Population
14.3.4.5.2	Shift from Baseline in Overall 12-Lead Electrocardiogram	Safety Population
14.3.4.5.3	Shift from Baseline in 12-Lead Electrocardiogram by Parameter	Safety Population
14.3.4.5.4	Pregnancy Test (Women of Childbearing Potential)	Safety Population

Listings:

Listing No.	Listing Title	Analysis Population
16.2.1.1	Screen Failures	All Subjects
16.2.1.2	Randomization	Safety Population
16.2.1.3.1	Disposition	All Randomized Subjects
16.2.1.3.2	Disposition	All Randomized Subjects
16.2.1.4	Analysis Sets	All Randomized Subjects
16.2.2.1	Study Deviations	Safety Population
16.2.2.2	COVID-19 Related Study Deviations	Safety Population
16.2.2.3	Missed Visit or Assessment Due to COVID-19	Safety Population
16.2.2.4	COVID-19 or Related Events Study Disruptions	Safety Population
16.2.2.5	COVID-19 Testing	Safety Population
16.2.4.1	Demographics and Baseline Characteristics	Safety Population
16.2.4.2	Baseline Disease Characteristics	Safety Population
16.2.4.3	Viral Serology at Screening	Safety Population
16.2.4.4	Tuberculosis Monitoring (TB)	Safety Population
16.2.4.5	Serum IgG and IgM Assessments	Safety Population
16.2.4.6	Medical and Surgical History	Safety Population
16.2.4.7	Rheumatic Disease History	Safety Population
16.2.4.8	Inclusion and Exclusion Criteria Deviation	All Enrolled
16.2.4.9	Prior Medications	Safety Population
16.2.4.10	Concomitant Medications	Safety Population
16.2.4.11	Pre-Medication	Safety Population
16.2.4.12	Rescue Medications/Re-dosing Medications	Safety Population
16.2.5.1	Study Drug Administration I	Safety Population
16.2.5.2	Study Drug Administration II	Safety Population
16.2.6.1	ADA, Nab and Titer	Immunogenicity Population
16.2.6.2	Time Matched of Rituximab Concentration	TMRC Population

16.2.7	All Non-Treatment Emergent Adverse Events	Safety Population
16.2.7.1	All Treatment Emergent Adverse Events	Safety Population
16.2.7.2	Treatment Emergent Serious Adverse Events	Safety Population
16.2.7.3	Treatment Emergent Adverse Events by Relationship	Safety Population
16.2.7.4	All Treatment Emergent Adverse Events Leading to Treatment Discontinuation	Safety Population
16.2.7.5	All Treatment Emergent Adverse Events Leading to Death	Safety Population
16.2.7.6	All Treatment Emergent Adverse Events Classified as Hypersensitivity Reactions	Safety Population
16.2.7.7	All Treatment Emergent Adverse Events Classified as Anaphylactic Reactions	Safety Population
16.2.7.8	All Treatment Emergent Adverse Events Classified as Infusion Related Reactions (IRR)	Safety Population
16.2.7.9	Events of Special Interest (EOSI)	Safety Population
16.2.7.10	Serious Events of Special Interest (EOSI)	Safety Population
16.2.7.11	All Treatment Emergent Adverse Events Attributable for Rescue Medication	Safety Population
16.2.8.1	Laboratory Results – Hematology	Safety Population
16.2.8.2	Laboratory Results – Biochemistry	Safety Population
16.2.8.3	Laboratory Results – Urinalysis	Safety Population
16.2.9.1	Vital Signs	Safety Population
16.2.9.2	Physical Examination	Safety Population
16.2.9.3	12-Lead Electrocardiogram	Safety Population
16.2.9.4	Pregnancy Test	Safety Population

Statistical Analysis Plan (SAP) Client Approval Form

Client:	[name] S.A.
Protocol Number:	RI-01-007
Document Description:	Final Statistical Analysis Plan
SAP Title:	A Randomized, Double-Blind, Parallel Group, Multicenter Study to Assess the Immunogenicity and Safety of Transitioning Subjects with Rheumatoid Arthritis to Biosimilar Rituximab (DRL_RI) or Continued Treatment with Rituxan® or MabThera®
SAP Version Number:	2.0
Effective Date:	CI

CI

Approved by:

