3.2.2 Contingency Measures Taken During the COVID-19 Pandemic

Based upon the above mentioned considerations, the following measures have been implemented in the study:

1. COVID-19 protective measures: Advice to the sites to implement general hygienic measures for both ongoing subjects and any new subject to educate on such protective and preventive measures.
2. Assurance of subject safety by investigator before enrolment (by COVID-19 related screening questionnaire).
3. Measures to be taken if investigator suspect COVID-19-related symptoms or if a subject is found positive to COVID-19.
4. In order to protect subject's safety and welfare, it is also recommended that site contacts subjects periodically (preferably on Day 7, 14; Weeks 6, 10, 14, 18, and 22) via telephone to inquire about his/her overall well-being, to seek information on alarm symptoms (fever, cough, breathlessness, COVID-19-related skin lesion, etc) of COVID-19 infection, information on subject's contact with any COVID-19-positive patient, and to guide the subject to take appropriate medical care.

If a study subject has an event suspected to be COVID-19 related, the investigator will have to decide on performing COVID-19 testing per local health authority or study site guidance.

Any new AE or change in the intensity of ongoing AE(s) with special focus on symptoms related to COVID-19, new medication(s) taken by the subject since his/her last visit, or any change in dose/frequency of medication(s), which is received, will be also documented in the source documents and eCRF.

5. Any event of COVID-19 is to be considered as an “Event of Special Interest” and all relevant detailed information will be collected, such as diagnosis, management and outcome. All events related to or linked to COVID-19 and meeting SAE criteria must be reported to **CI** Pharmacovigilance within 24 hours of the investigator’s knowledge of the event by facsimile or other appropriate method.

Moreover, due to current COVID-19 pandemic situation, remote source data verification may be performed per local regulations. All details of remote monitoring will be captured in the monitoring plan, if required.

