9.1.2. Relationship of Adverse Events to Study Drug

The investigator will provide an assessment of the relationship of the event to the study drug. The possible relationships are “Related” and “Not Related”.

The drug-related TEAE data will be presented by SOC and PT in a manner similar to that described in [Section 9.1.1](#).

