9.2. Event of Special Interest (EOSI)

Any event of COVID-19 is to be considered as an “Event of Special Interest (EOSI). All EOSI classified by System Organ Class (SOC) and Preferred Term (PT) according to the Medical Dictionary for Regulatory Activities (MedDRA, Version 23.0 or higher or available latest version).

All EOSI will be summarized and presented in a listing for the safety population.

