9.2.1. Severity of Event of Special Interest (EOSI)

A summary of EOSI by CTCAE grade will be presented in a table. The possible severities are ‘Mild’, ‘Moderate’, ‘Severe’, ‘Life-threatening’ and ‘Death related to AE’. In the EOSI severity table, if a subject reported multiple occurrence of the same EOSI, only the most severe will be presented.

The severity of the EOSI will be graded based on the Common Terminology Criteria for Adverse Events (CTCAE) v5.0. A summary of EOSI will be provided by treatment arm Adverse events will be presented by SOC, PT and CTCAE grade in a manner similar to that described in [Section 9.2](#)

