9.2.2. Serious Event of Special Interest (EOSI)

The Serious EOSI data will be presented by SOC and PT in a manner according to the Medical Dictionary for Regulatory Activities (MedDRA, Version 23.0 or higher or available latest version). All Serious EOSI will be summarized and presented in a listing for safety population.

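### The SAP promises summaries of all COVID-19 events of special interest, but both EOSI tables in its index are restricted to study-drug-related events

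*SAP*

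**What the plan says.** Protocol 3.2.2 sets the definition: every COVID-19 case falls in the special-interest category. For these cases the protocol requires that "all relevant detailed information will be collected, such as diagnosis, management and outcome". SAP 9.2 repeats the definition. Neither document makes causality part of it.

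The SAP text then commits to three summaries:

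- SAP 9.2: "All EOSI will be summarized and presented in a listing for the safety population".
- SAP 9.2.1: "A summary of EOSI by CTCAE grade will be presented in a table". The same section adds presentation by treatment arm and by SOC, PT and grade.
- SAP 9.2.2: "All Serious EOSI will be summarized and presented in a listing for safety population".

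The table index in SAP 12.2 contains two EOSI tables:

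- 14.3.1.2.10.1: "Study Drug-Related Events of Special Interest (EOSI) by System Organ Class, Preferred Term and CTCAE Severity".
- 14.3.1.2.10.2: "Study Drug-Related Serious Events of Special Interest (EOSI) by System Organ Class, Preferred Term and CTCAE Severity".

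The index also has two EOSI listings, 16.2.7.9 (EOSI) and 16.2.7.10 (serious EOSI). Neither title mentions relationship to study drug. SAP 10.1, which records changes from the protocol, mentions only the addition of estimands.

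**The concern.** The text and the index of the same SAP specify different outputs. The text asks for all EOSI; the index delivers only those attributed to study drug. A programmer working from the index would apply a causality filter that SAP 9.2 to 9.2.2 do not contain, and the tables would cover a different set of events from the matching listings.

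The filter depends on a judgement. SAP 9.1.2 states: "The investigator will provide an assessment of the relationship of the event to the study drug". The answer is binary, related or not related. Protocol 6.3.1.4 tells the investigator to consider alternative causes, and community exposure during a pandemic is one.

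What is at stake is a descriptive comparison of COVID-19 frequency and severity between the DRL_RI arm and the continued-reference arm. SAP 9.2.1 promises it, and a table limited to related events cannot supply it.

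**Working it through.** The plan states no figure on this point, so there is none to reproduce. The check is a comparison of the SAP text with its index, followed by a simple bound.

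**Step 1. Text against index.**

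| Promised in the text | Causality condition in the text | Table in SAP 12.2 | Restriction in the title |
|---|---|---|---|
| All EOSI summarised (9.2) | None | 14.3.1.2.10.1 | Drug-related only |
| EOSI by CTCAE grade and arm (9.2.1) | None | 14.3.1.2.10.1 | Drug-related only |
| All serious EOSI summarised (9.2.2) | None | 14.3.1.2.10.2 | Drug-related only |

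EOSI tables in the index: 2. Restricted to related events: 2 of 2. Covering all EOSI: 0. EOSI listings: 2, neither restricted.

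**Step 2. Does the rest of the index suggest the restriction is deliberate?** It points the other way.

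- General TEAEs have an all-causality table (14.3.1.2.1) and a related-only table (14.3.1.2.2).
- Serious TEAEs have the same pair (14.3.1.2.4 and 14.3.1.2.5).
- The hypersensitivity, infusion-reaction and anaphylaxis tables break events down by relationship or by grade; none is filtered on relationship.
- EOSI alone has the related-only tables without all-causality partners.

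**Step 3. Does another table supply the missing summary?**

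- The adverse event overview in SAP 9.1.1 has 18 rows, and none is for EOSI.
- Table 14.3.1.2.3 gives all TEAEs by SOC, PT and grade. Treatment-emergent COVID-19 events are in it but are not identified as EOSI. Subjects are counted once per SOC and PT, so if COVID-19 is coded to more than one PT, no row gives the number of subjects with any EOSI.
- Table 14.3.1.2.4 gives serious TEAEs by SOC and PT without grade. Serious EOSI of any causality by grade therefore appear in no listed table.
- Tables 14.1.1.5 and 14.1.1.6 concern COVID-19 deviations and missed visits or assessments, not the events themselves.

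**Step 4. Size.** Let N be the number of subjects with an EOSI and r the proportion of them whose event is rated related, taking one event per subject. Then:

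- subjects shown in the EOSI table = r × N
- subjects omitted = (1 − r) × N

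The documents give neither N nor r. As an assumption for scale only, let 5% to 10% of the 140 planned subjects have a COVID-19 event:

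- N = 140 × 0.05 = 7 to 140 × 0.10 = 14, or on average 3.5 to 7 per arm.
- With r = 0, the table shows 0 subjects and omits 7 to 14.
- With r = 1, the table shows 7 to 14 and omits 0.

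The omitted share, 1 − r, is bounded only by 0% and 100%.

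**The case against.** **The information is still reported.** Listings 16.2.7.9 and 16.2.7.10 hold all EOSI and all serious EOSI. Treatment-emergent cases also enter the all-causality TEAE tables, SAP 9.2.3 plans a listing of EOSI leading to death, and COVID-19 tests are listed (16.2.2.5). With few cases, a reader could count them by hand. This stands, and it limits the seriousness of the point: what is missing is the dedicated by-arm summary, not the data.

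**It may be only a slip in two titles.** SAP 12.2 lists titles, and the table shells that the SAP mentions are not in the documents. The body text is clear, so the programming may be right. That is possible, but the documents cannot show it, and nothing in the SAP says which source prevails.

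**The protocol does not demand the table.** Protocol 3.2.2 makes COVID-19 listings and summaries conditional on need and lets the sponsor stop COVID-specific collection if the pandemic wanes. This is correct. The unconditional commitment is the SAP's own, and that is the one its index fails to meet.

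Three stronger readings are tempting, and the documents support none of them:

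- *A reader might infer that most COVID-19 events would be omitted and the tables left nearly empty.* No expected share of related events is given. Protocol 6.3.1.4 asks investigators to weigh mechanism of action and class effect as well as alternative causes, and Protocol 3.2.1 calls rituximab a known immunosuppressant, so the related share need not be low.
- *A reader might infer that the general TEAE tables scatter COVID-19 over several preferred terms.* The SAP names the MedDRA version but does not say how COVID-19 will be coded.
- *A reader might infer that an unfiltered table would settle whether rituximab raises COVID-19 risk or severity*, the uncertainty raised in Protocol 3.2.1. Both arms receive a rituximab product, so the table can only describe differences between DRL_RI and the reference product.

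**Conclusion.** The contradiction holds on the text alone. SAP 9.2 to 9.2.2 promise all-causality EOSI summaries, both EOSI tables in SAP 12.2 are limited to study-drug-related events, and SAP 10.1 does not explain the limit. Under the index, every EOSI rated not related is absent from the EOSI tables, and the by-arm account of COVID-19 frequency and severity is not produced. The proportion absent is unknown, from 0% to 100%.

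The conclusion assumes that the table titles describe the programmed content. If the unseen shells already include all EOSI, only the titles need correcting.

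The point is minor to moderate. It concerns the specification of one safety summary. It does not touch the ADA or NAb endpoint, the overall TEAE and SAE counts, or the hypersensitivity, infusion-reaction and anaphylaxis tables.

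**What to change.** 1. Remove the words Study Drug-Related from the titles of Tables 14.3.1.2.10.1 and 14.3.1.2.10.2, so that they cover all EOSI and all serious EOSI by SOC, PT and CTCAE grade, by treatment arm.
2. Add one line to each table giving the number and percentage of subjects with any EOSI (any serious EOSI in the second), by arm.
3. If related events are wanted separately, show them as a subset, following the pairing already used for 14.3.1.2.1 with 14.3.1.2.2 and for 14.3.1.2.4 with 14.3.1.2.5.
4. Check that the shells and programming specifications match SAP 9.2 to 9.2.2.

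The cost is two title edits, removal of a filter if one has been programmed, and one summary line per table. No new data are needed, because relationship, seriousness and grade are already collected for each event. It is best done before database lock: under SAP section 1, a later departure from the SAP needs an addendum and an explanation in the study report.
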